The OBJECTIVE of this research protocol is to evaluate the effectiveness of RPP compared to postural drainage plus compression to the muscle belly of the upper limbs, as an adjuvant treatment for children with pneumonia. It is expected that the clinical severity decreases by 1.5 in the Wang score (a modification of the Silverman score), with a standard deviation of 2.6 points and a decrease of two days in the hospital stay with a α 0.05 in a one-tail test, a P of 80% and a 95.5% confidence interval.

METHODOLOGY, the protocol design corresponds to a single-blind trial. The population will consist of children aged from 0 to 8 years old diagnosed with pneumonia with a development time less than 7 days. The participants who comply with the selection criteria will be grouped in blocks of two using a randomization software (www.radomization.com).

The sample calculation corresponds to 40 participants per group. The intervention group will be exposed to techniques such as prolonged slow expiration, controlled expiratory flow exercises, tracheal pumping and tracheal reflex. The control group will be subject to postural drainage plus compressions to the muscle belly of the upper limbs. Both groups will go through 10 sessions: One daily session from Monday to Friday with a duration of 10 to 15 minutes each.

The Wang score (a modification of the Silverman score) will be used to measure the clinical severity and a pulse oximeter ChoiceMMed MD300C5 for SpO_2 and heart rate readings, the medical records will be consulted during the hospital stay.

DATA ANALYSIS PLAN, to prove whether there are or not statistical differences in and between both groups a Mann-Whitney U test will be used. The weightings from the Wang score (a modification of the Silverman score) will be considered before and immediately after the intervention maneuvers, and after 15, 30 and 120 minutes after said maneuvers have been performed.

BACKGROUND

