To evaluate the prolonged effects (15, 30 and 150 minutes after intervention) of RPP on clinical severity (Wang score (a modification of the Silverman score)) in comparison to PD plus muscle belly compressions to the upper limbs for the treatment of a child with in-hospital pneumonia.

To evaluate the effect of RPP compared to PD plus muscle belly compressions to the upper limbs on the number of days of HS of children with pneumonia.

HYPOTHESIS

1. Children with pneumonia who receive RPP Will have a decrease of 1.5 points, with a standard deviation of 2.6 In the Wang score (a modification of the Silverman score), 30 minutes after it being performed.

2. Children with pneumonia will have a decrease in HS of two days, compared to those treated with PD plus muscle belly compressions to the upper limbs.

METHODOLOGY AND RESEARCH DESIGN

DESIGN

Single-blind randomized clinical trial

Population

1. Study universe: Hospitalized children with pneumonia at the infectiology service.

2. Study population: Children from 0 to 8 years old with a diagnostic of pneumonia (under WHO's criteria) with a development time less than 7 days.

3. Sample: With the support of the epidemiology department, a daily list of all new cases of pneumonia will be provided. Patients then will be included once the diagnostic established by the pneumonia infectiology service is obtained.

Sample size calculation

The calculation for a sample size for an error of α 0.05 in a one-tail test and a power of 80% is based on the values described by Postiaux^{*37} in the difference between the groups 30 minutes after the intervention, during 10 sessions. The difference in the Wang score (a modification of the Silverman score) measurements between the two groups was of 1.5 points with a standard deviation of 2.6 points.

 $\label{eq:states} \begin{array}{l} \Delta \texttt{= 1.5} \\ \texttt{S= 2.6} \\ \texttt{n = 2S}^2(\texttt{Z}_{\alpha/2} + \texttt{Z}_\beta)/\Delta^2 \end{array}$

The participants' sample size will be of 40 per group, to obtain statistical differences in the decrease of the Wang score (a modification of the Silverman score) entre between both groups with a α 0.05 in a one-tail test and a power of 80%, considering a decrease of 36% and a standard deviation of 13%.

Randomization

- 1. A sequence of aleatory numbers in blocks of 2 will be generated in each of the study groups using the software randomization.com, done by a person foreign to the research.

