- 2. Using the randomized numbers generated by the software, it will be decided what group each participant belongs to (control or intervention) and what maneuver will be assigned to them.
- 3. These numbers and their maneuvers will be placed inside dark envelopes.
- 4. The whole randomization and assignment sequence will be performed by a person foreign to the research and without the knowledge of the researchers. Support will be provided from the coordination for nursing research, who will select the personnel for the process.

Blinding

After the assignment of the procedure, it will be blinded for the collaborator capacitated to measure the Wang score (a modification of the Silverman score), heart rate, SaO_2 and registering the days of hospital stay posterior to the pneumonia diagnosis. Data capture will be performed by the personnel previously selected by the coordination for nursing research, without the knowledge of the researchers.

Selection criteria

Inclusion criteria:

1. Patients from the HIMFG with diagnosis of pneumonia (considering the diagnostic criteria of the WHO and the Guidelines for Nosocomial Pneumonia from the infectiology department at the HIMFG) registered by the department of in-hospital epidemiology:

- 1.1. Diagnostic criteria:
 - a. Radiological, clinical and from laboratory:
 - 1. Radiology: Counting with at least one of the following findings:
 - 2. New, progressive or persistent infiltrate.
 - 3. Consolidation.
 - 4. Cavitating.
 - 5. Pneumatocele in children younger than 1 year old.

b. Signs, symptoms and laboratory data:

At least one of the following findings.

1. Core temperature > 38.5° C o < 36° C (or rectal temperature > $38 C^{\circ}$ for at least 30 minutes after discarding the cause of external overheating, for example: overclothing)

2. Tachycardia (with no evident clinical cause) >2 standard deviation for the age and persistent (30 to 60 minutes) o bradycardia in children < 1 year old defined as a heart rate <10 percent for the age (in absence of vagus nerve stimulation, β -blockers or congenital heart defect).

3. Tachypnea defined as a respiratory frequency >2 standard deviation for the age or requirement of mechanical ventilation due to an acute process not related to an underlaying neuromuscular disease or secondary to general anesthesia.

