- 2. Days of hospital stay from the beginning of the pneumonia.

Confounding variables

- 1. Baseline disease.
- 2. Age.
- 3. Nutritional state.

Descriptive variables

- 1. Sex.
- 2. Reasons for check-in.
- 3. Heart rate.
- 4. Oxygen saturation (SaO2).
- 5. Lung occupancy.
- 6. Wang score.

Variables	Туре	Instrument	Range
Clinical severity.*	Ordinal.	Wang score.	0-12 pts.
Heart rate.*	Discrete quantitative.	Pulse oximeter. ChoiceMMed MD300C5.	30bpm to 325bpm.
SaO ₂ .*	Discrete quantitative.	Pulse oximeter . ChoiceMMed MD300C5.	0% to 100%.
Lung occupancy.**	Nominal.	Simple X-ray of the thorax.	Identification of the percentage occupied by secretions and infiltrates, detect complications (atelectasis, effusion ,etc).
Days of hospital stay from the beginning of the pneumonia.**	Discrete quantitative.	Clinical file.	0-180 days.
Age.***	Discrete quantitative.	Clinical file.	1 to 6 years 364 days old.
Sex.***	Nominal	Clinical file.	Masculine/femenine.
Baseline disease.	Nominal.	Clinical file.	Yes/No Specify.
Reason for check-in.***	Nominal	Clinical file.	Specify.
Complications of pneumonia from the momento of inclusion.***	Nominal.	Clinical file.	None/ Effusion/ Necrosis or pulmonary abscess/ Other (specify)

*Measurements must be performed before intervention, immediately after, and 15, 30 and 150 minutes after. **Measurements will be performed before

initiating treatment sessions and after they conclude. *** Measurements will be developed previously to the randomized group assignation.

GENERAL DESCRIPTION OF THE STUDY

Assessment prior to the study

- 1. All patients diagnosed with pneumonia who comply with the selection criteria will be invited to participate in the study, in case of accepting, those older than 8 years old will verbally agree and will be given forms of informed consent to sign.
- 2. Data obtained will be documented in a previously established data collection format (Anex 2).
- 3. If there is no contraindication for the procedure, then the maneuver will be assigned.

Initiation and evaluation of the assigned maneuver

- 1. The researcher will perform the maneuver according to group assignation.
- 2. Subsequently a collaborator, previously blinded to the maneuver and standardized for the Wang score (a modification of the Silverman score), will evaluate the Wang score 15, 30 and 150 minutes after its application.

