- 3. Another collaborator will do a follow-up on the patients in order to register their hospital stay time posterior to the diagnosis of pneumonia.
- 4. The assigned maneuver will be performed once a day on the patient.

End of study

The study will end once the patient checks out of the hospital.

Quality control

The assessment of the efficiency will be performed by 2 collaborators blinded to the maneuver. One collaborator will assess the Wang score (a modification of the Silverman score), heart rate and SaO_2 and the other collaborator will register the days of HS.

DATA ANALYSIS PLAN

Descriptive statistic: There will be an assessment of the central tendency values, relative dispersion and disposition to evaluate the descriptive variables at the start and at the end of the studyin both groups, as well as the dependent variables after the intervention.

Inferential statistic:

- 1. The comparison in score of the descriptive variables in and between the groups will be performed using a Mann-Whitney U test.
- 2. A 95% confidence Interval is estimated.

The Wang score rates will be assessed in the measurements made before and immediately after the intervention, and 13, 30 and 150 minutes after.

To describe the measurement differences and to reject or not the hypothesis, a Mann-Whitney U test will be used.

LIMITATIONS OF THE STUDY

Due to the maneuver condition, the subject cannot be blinded, and only the researchers will be single-blinded, which confers a type of bias to the study.

TIMELINE

The timeline of activities is presented as a FORMAT ATTACHED to this document.

ETHICAL CONSIDERATIONS

The 2016 guide for the evaluation of ethical considerations of our institution is presented as a FORMAT ATTACHED to this document.

Beneficence/Nonmaleficence

This is a MAXIMUM TO MINIMAL RISK study for participants, and it could cause reflux, vomit or irritability of the patient's emotional state (with all that implies). Potential benefit to the patient by improving their clinical severity and reducing the days of hospital stay. Potential Benefit to society by reducing the days of hospital stay, which in turn will reduce the cost of treatment for children with pneumonia.

Autonomy and respect

It will be clearly expressed to the patient or person responsible for them, every procedure they will become subject to, until their understanding is secured.

A Form of Informed Consent will be required (Anex 3).

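### Fixed blocks of two at a single hospital let anyone who follows the assignments in order deduce up to 40 of the 80 before the envelope is opened

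*Combined protocol and SAP*

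**What the plan says.** The Methodology paragraph of the Summary reads: "The participants who comply with the selection criteria will be grouped in blocks of two using a randomization software". The Randomization section gives the same size: "A sequence of aleatory numbers in blocks of 2 will be generated in each of the study groups". Neither place mentions a second block size, random variation of the size, or strata. The trial recruits at one hospital and plans 40 children per group.

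For concealment, a person outside the research prepares the sequence without the researchers' knowledge, and "These numbers and their maneuvers will be placed inside dark envelopes". Sealing and sequential numbering are not mentioned.

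Under Initiation and evaluation of the assigned maneuver, "The researcher will perform the maneuver according to group assignation". Limitations of the study nevertheless says that "the subject cannot be blinded, and only the researchers will be single-blinded".

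Some text limits discretion over who enters. The Population section says "a daily list of all new cases of pneumonia will be provided". Assessment prior to the study says "All patients diagnosed with pneumonia who comply with the selection criteria will be invited to participate in the study", and places consent and a contraindication check before allocation: "If there is no contraindication for the procedure, then the maneuver will be assigned".

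**The concern.** In a 1:1 block of two, the first assignment fixes the second. An outside list-maker and opaque envelopes protect the list itself, but not an inference from an assignment already observed. The block size is printed in the protocol, and the researcher who performs the maneuver necessarily knows the arm. The statement in Limitations that the researchers are blinded cannot hold for that person and should be reconciled with the treatment section.

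Allocation concealment is what is at stake. If the person who screens, obtains consent or times entry is the treating researcher, or talks to that researcher, the next arm may be known while the contraindication check and the moment of entry are still open. Children could then be entered, deferred or timed according to the arm they would get. The arms could differ at baseline in ways that blinded outcome scoring does not correct.

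**Working it through.** **Inputs.** Block size 2 (Summary; Randomization). Sample size 40 per group, so 80 in total, allocated 1:1 (Sample size calculation). One hospital (Inclusion criteria). The treating researcher learns each assignment (Initiation and evaluation of the assigned maneuver).

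**The plan's own figure.** The total of 80 rests on 40 per group. With a difference of 1.5, an SD of 2.6, one-sided α of 0.05 and 80% power, the standard formula gives 2 × 2.6² × (1.645 + 0.842)² / 1.5² = 37.15, or 38 per group. The stated 40 is consistent with this. A two-sided test would need 48.

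**Predictability with one fixed block size.** For blocks of size 2k, with every earlier assignment seen:

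- share known with certainty = 1/(k + 1)
- share guessed correctly = [k + (4^k / C(2k, k) − 1)/2] / (2k)

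For k = 1, the certain share is 1/2, which is 40 of 80. The correct share is [1 + (4/2 − 1)/2]/2 = 0.75, which is 60 of 80. Simple randomization would give 0 certain and 40 of 80 correct. Full enumeration of the blocks gives the same result for size 2.

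**If not every first assignment is seen.** The protocol does not say how often the first of a pair is seen before the second child enters. Call that share f. Then the certain share is f/2 and the correct share is 0.5 + 0.25f. The values of f are assumptions.

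| f | Certain, of 80 | Guessed correctly |
|---|---|---|
| 100% | 40 | 75% |
| 50% | 20 | 62.5% |
| 25% | 10 | 56% |

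**Alternatives, all assignments seen.** The mixed-block row comes from 3,000 simulated lists of 80. Sizes were equally likely, and the observer knew the set of sizes but not their order.

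| Scheme | Certain | Guessed correctly |
|---|---|---|
| Fixed 2 (plan) | 50% (40 of 80) | 75% |
| Fixed 4 | 33% (26.7 of 80) | 71% |
| Fixed 6 | 25% (20 of 80) | 68% |
| Fixed 8 | 20% (16 of 80) | 67% |
| Random 4/6/8 | 2.3% (about 2 of 80) | 68% |
| One permuted list of 80 (k = 40) | 2.4% (about 2 of 80) | 56% |

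Larger fixed blocks alone still leave 16 to 27 assignments certain. Varying the size removes most of the certainty, while overall guessing improves by only about 7 points.

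**Balance given up.** Blocks of two keep the arms within one child throughout. Mixed 4/6/8 blocks allow a gap of at most 4, and the gap is 2 or more at 40 enrolled in about 27% of lists. With a single permuted list, the number in one arm at 40 enrolled is hypergeometric (80, 40, 40), with variance 40 × 0.5 × 0.5 × 40/79 = 5.06. The gap between arms therefore has SD 2 × √5.06 = 4.50, with a 12% chance of 8 or more and a 4% chance of 10 or more.

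**The case against.** The strongest reply is that the harm is conditional. It needs whoever controls entry to know the preceding assignment before the next child enters, and nothing in the protocol shows that this person and the treating researcher are the same. Discretion is also limited. New cases come from the epidemiology department, the infectiology service makes the diagnosis that triggers inclusion, and all eligible children are to be invited. Many exclusions are largely objective, such as mechanical ventilation or pleural effusion. Age, sex and reason for admission are recorded before allocation. The Wang score, heart rate, saturation and hospital stay are recorded by blinded collaborators.

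Much of this stands as a limit on size. Forty of 80 is an upper bound, and the route to bias examined here is selection at entry, not outcome scoring. It does not answer the point, because none of these safeguards conceals the next assignment. Judgement remains, for example over hemodynamic instability, which has no threshold, and over when a deferred child enters. The variables table requires the Wang score before the intervention, not before allocation. Annex 2, which might say more, is not in the text available.

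Two further objections deserve credit. First, the block size is called fixed only because one size is stated, and the Randomization section's phrase about generating blocks within each study group is unclear. No strata are named, however, and if there were strata the same inference would work for someone following each one. Second, the remedy cuts guessing only from 75% to 68% and gives up near-perfect balance. That is correct; the gain lies in certainty, from 40 known assignments to about 2.

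**Conclusion.** The point holds and should be fixed. With the only block size the protocol gives, up to 40 of 80 assignments can be deduced in advance and a best guess is right 75% of the time. The upper bound assumes one unstratified list used in order, knowledge of the block size, and sight of every first-of-pair assignment before the second child enters. With 25% to 50% seen, 10 to 20 assignments are certain. The predictability follows directly from the design. Its exploitation is possible but not shown, and no effect on the Wang difference or the error rate has been estimated.

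**What to change.** - Have the same outside person regenerate the list with randomly varied blocks of 4, 6 and 8, chosen to sum to 80. Keep the sizes out of the document the research team uses.
- Number the envelopes in sequence and make them sealed and opaque. Open each only after consent, eligibility and the pre-session Wang score are recorded. Consent and the contraindication check already precede allocation; the numbering, the sealing and the Wang score before opening are additions to the text.
- In the same amendment, say who screens, consents and times entry and whether that person learns assignments, and reconcile the blinding statement in Limitations with delivery by the researcher.

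The cost is one regenerated list and one amendment. If enrolment has begun, which the protocol does not establish, the change covers only the remaining assignments, and the block sizes should sum to that number. Stopping mid-block could leave the arms up to 4 children apart. Lists simply cut at 80 would differ by 2 or more in about 27% of cases, which block sizes summing to 80 avoid. A single permuted list of 80 resists guessing better (56% correct), but at 40 enrolled the gap could reach about 9 children (2 SD). Varied blocks are the cheaper compromise.

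### Hypothesis 1 states the 1.5-point fall in Wang score without a comparator, although the trial is sized on 1.5 as a between-group difference, and the analysis plan does not say which contrast decides it

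*Combined protocol and SAP*

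**What the plan says.** In HYPOTHESIS, item 1 is "Children with pneumonia who receive RPP Will have a decrease of 1.5 points, with a standard deviation of 2.6" on the Wang score, "30 minutes after it being performed". No control group appears in it. Item 2, directly below, does name one: the children "will have a decrease in HS of two days, compared to those treated with PD plus muscle belly compressions to the upper limbs". The OBJECTIVE paragraph of the SUMMARY again gives the 1.5 points (SD 2.6) as a plain expected decrease.

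Sample size calculation gives the same two figures another meaning. They are taken from an earlier trial, "in the difference between the groups 30 minutes after the intervention, during 10 sessions", and the difference in Wang score "measurements between the two groups was of 1.5 points with a standard deviation of 2.6 points".

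Research question 1, the general objective and the first specific objective all compare RPP with postural drainage plus muscle belly compressions.

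DATA ANALYSIS PLAN says that the comparison of the descriptive variables "in and between the groups will be performed using a Mann-Whitney U test". The list of research variables counts the Wang score among the descriptive variables as well as naming clinical severity as a dependent variable. The SUMMARY and the section on variables and measuring instruments also plan Wang comparisons both within and between groups. A later sentence of the analysis plan says that a Mann-Whitney U test will be used to reject or not reject the hypothesis. It gives no null hypothesis, contrast or deciding time point. The section on products of the study makes dissemination conditional on results that do not reject the hypothesis.

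**The concern.** One pair of figures describes two different quantities: a fall in treated children and a difference in outcome between treated and control children. Only the second measures an effect of RPP. Both arms receive usual pneumonia treatment and a hands-on session of the same length, so part or all of any fall in the RPP arm could also occur in the control arm.

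If hypothesis 1 is judged as worded, a before-after fall in the RPP arm satisfies it whatever the control arm does. Because the plan allows within-group comparisons and does not say which contrast decides, that choice could be made after the data are seen. An ineffective maneuver could then be reported as confirmed.

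**Working it through.** **Inputs from the sample size section:** difference 1.5, SD 2.6, one-tailed alpha 0.05, power 80%, 40 per group. Hence z(alpha) = 1.645, z(beta) = 0.842 and (1.645 + 0.842)² = 6.183.

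**1. Which meaning of 1.5 gives the stated 40?**

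- Two-arm difference, one-tailed: n = 2 × 2.6² × 6.183 / 1.5² = 37.15, so 38 per group. This is within two of 40.
- Fall in one arm, one-tailed: n = 2.6² × 6.183 / 1.5² = 18.6, so 19 children. This is not close to 40.
- Two-arm difference, two-tailed: 47.2, so 48 per group. This does not match either.

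The trial was therefore sized on the between-group meaning. (The formula as printed does not square the sum of z values and uses the two-sided z. The calculation above uses the standard squared form with the one-tailed z.)

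**2. Power with the hypothesis worded as between-group.** Standard error = 2.6 × √(2/40) = 0.581. Power = Φ(1.5/0.581 − 1.645) = Φ(0.935) = 82.5%, or 81.9% with the t distribution.

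**3. Illustration of the literal reading.** The assumptions, none of them in the documents, are: RPP effect zero, both arms fall by the same amount c, and SD of within-child change 2.6. The standard error of the mean fall in 40 RPP children is 2.6/√40 = 0.411. The chance that a one-sided test of any fall is significant is Φ(c/0.411 − 1.645).

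| Shared fall c | c/0.411 | Normal | t distribution |
|---|---|---|---|
| 1.5 | 3.65 | 97.7% | 97.4% |
| 1.0 | 2.43 | 78.5% | 77.2% |
| 0.5 | 1.22 | 33.4% | 32.6% |

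The SD also matters. For c = 1.0 the t-based figure runs from 99.9% at SD 1.3 to 55% at SD 3.5; for c = 0.5, from 77% to 22%. In simulation with c = 1.5, the one-sided between-arm Mann-Whitney U test was significant in about 5% of trials, as it should be when RPP has no effect.

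**4. The named test applied within the arm.** Suppose the Mann-Whitney U test is run on before and after scores in the RPP arm as if they were independent samples. In simulations with rounded 0–12 scores, an assumed baseline mean of 6, SD 2.6 at each occasion and a shared fall of 1.5, it was significant in about 80% to 94% of trials for within-child correlations from 0 to 0.75. For smaller falls with zero correlation, the normal approximation Φ(c/0.581 − 1.645) gives about 53% at c = 1.0 and 22% at c = 0.5.

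**5. The wording about not rejecting the hypothesis.** If the hypothesis tested is that the fall in the RPP arm equals 1.5 (two-sided 5% test, SD 2.6, 40 children), it is not rejected in about 95%, 79% or 35% of trials when the true fall is 1.5, 1.0 or 0.5. None of these figures depends on what the control arm does.

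**The case against.** The comparative intention is plain from the research question, the objectives and the sample size section, which speaks of "The participants' sample size will be of 40 per group, to obtain statistical differences in the decrease of the Wang score" between both groups. Hypothesis 2 is clipped in the opposite way: it names the comparator but does not say that the children concerned receive RPP. This looks like loose drafting or translation. A reader might infer that the trial sets out to test a single-arm hypothesis, or that a within-group fall is its criterion for success. The documents support neither: planning within-group comparisons is not the same as making them decisive.

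The Mann-Whitney U test is also a test for two independent samples, and no one-sample or paired test is planned. A reader might take 97% as the trial's false-positive rate. It is not, because it belongs to a test outside the plan and to the most favourable of the three assumed falls. Nor do the documents say that both arms are expected to improve. They say only that both receive usual treatment, which need not lower the score by 1.5 points within 30 minutes.

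All of this stands as a limit on the size of the point. It does not remove the gap. The SUMMARY assigns the Mann-Whitney U test to differences within as well as between groups, so naming the test does not identify the contrast. The sentence on rejecting the hypothesis does not identify it either.

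**Conclusion.** The point holds as an inconsistency of wording with a possible, not certain, effect on the conclusion. Hypothesis 1 and the matching SUMMARY sentence leave out the comparator on which the trial was sized, and the analysis plan does not supply it.

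The firm parts are the text itself and the sample size check (38 by formula against 40 stated, on the between-group reading only). The percentages for a shared fall are illustrations. They rest on an assumed common fall and on reading 2.6 as the SD of within-child change, and at SD 2.6 they range from about 97% down to 33%. A between-arm Mann-Whitney U test, which is the likely intention, would hold the error at about 5%. The design and the sample size are not called into question.

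**What to change.** 1. Reword hypothesis 1, and the matching sentence in the SUMMARY, along these lines: *the Wang score 30 minutes after the maneuver falls 1.5 points more with RPP than with postural drainage plus muscle belly compressions.*
2. State the null hypothesis of no difference between the groups.
3. In DATA ANALYSIS PLAN, state that hypothesis 1 is judged only on the between-group Mann-Whitney U test at 30 minutes, and that within-group changes are descriptive.
4. Keep 2.6 as the SD used for the sample size, and say whether it refers to the change from baseline or to the 30-minute score. The documents do not say, so it should not be labelled an SD of change unless the source confirms it. Apply the deciding test to the same quantity.

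The cost is wording only. The 40 per group, the design and the named test all stay as they are.
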